1.7.4.1 Clinical Pharmacokinetics of LEE011

LEE011 is rapidly absorbed with median T_{max} ranging from 2-5 hours in both adult and pediatric patients. Plasma concentrations increased approximately 2- to 3-fold from C1D1 to C1D18 due to accumulation, with steady state being reached by approximately day 8. Mean effective $T_{1/2}$ was 32.6 hours in study CLEE011X2101. At steady state (C1D18/21), plasma exposure increases in LEE011 were slightly higher than dose proportional over the dose range 50-1200mg.

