6.3 LEE011 ADMINISTRATION SCHEDULE AND DOSE ADJUSTMENTS

LEE011 will be given orally once a day on days 1-21 of a 28 day cycle (3 weeks on / 1 week off). Days 22-28 will be a “rest” from LEE011.

Table 6.1 Dose and Treatment Schedule

Study Treatment	Pharmaceutical form and route of administration	Total Dose	Frequency and/or Regimen
LEE011	200 mg capsules by mouth	200,400, or 600 mg	Once Daily on Days 1-21 of a 28 day cycle. Rest Days 22-28

LEE011 will be administered as a flat-fixed dose, and not by body weight or body surface area.

The investigators will instruct the patient to take the study drug as per protocol. Patients must be instructed to return unused study drugs to the site at discontinuation or completion of treatment. The site personnel will ensure that dosing compliance is being performed by reviewing patient dosing diaries at each the end/start of a new treatment cycle.

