6.4 LEE011 DOSING

LEE011 must be taken as follows:

- Patients should be instructed to take the LEE011 capsules with a large glass of water (~250 mL or 8 oz.) at the same time each day;
- LEE011 can be taken without regard to meals; however dietary habits around the time of dosing should be as consistent as possible throughout the study;
- Patients should be instructed to swallow the LEE011 capsules whole and not to chew, crush or open them;
- If vomiting occurs during the course of treatment, no re-dosing of the patient is allowed before the next scheduled dose;
- Any doses that are missed (not taken within 6 hours of the intended time) should be skipped and should not be replaced or made up on a subsequent day;
- Patients must avoid consumption of grapefruit, Seville oranges or products containing the juice of each during the entire study and preferably 7 days before the first dose of study medication, due to potential CYP3A4 interaction with the study medications. Orange juice is allowed.

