Confounding factors and/or alternative causes for increased transaminases should be excluded before dose interruption/reduction. They include but are not limited to: concomitant medications, herbal preparations or dietary supplements, infection, hepato-biliary disorder or obstruction, new or progressive liver metastasis, and alcohol intake.	

QTC	
Toxicity/Grade	Dose Limiting Toxicity and Management Recommendations
For all grades	
 • Check the quality of the ECG • Perform analysis of serum electrolytes (K+, Ca++, Phos, Mg++). If below the lower limit of normal, interrupt LEE011 administration, correct with supplements or appropriate therapy as soon as possible, and repeat electrolytes until documented as normal • Review concomitant medication usage for the potential to inhibit CYP3A4 and/or to prolong the QT interval • Check compliance with correct dose and administration of LEE011
2 QTc 481-500 ms	
Interrupt LEE011
 
Perform a repeat ECG one hour after the first QTcF of ≥ 481ms
 
If QTcF < 481 ms, restart LEE011 at the same dose. No dose adjustment for the first occurrence
 
If QTcF remains ≥ 481 ms, restart LEE011 at the same dose level. No dose adjustments required for the first occurrence
 
If QTcF ≥ 481 ms recurs, dose limiting toxicity
 
Repeat ECGs 7 days and 14 days after dose resumption (then as clinically indicated) for any patient who has therapy interrupted due to QTcF ≥ 481 ms

3 QTc ≥ 501 ms on at least two separate ECGs	
Interrupt LEE011
 
 • Consider consulting a local cardiologist

	
 • Perform a repeat ECG one hour after the first QTcF of ≥ 501 ms • If QTcF remains ≥ 501 ms, repeat ECG as clinically indicated, but at least once a day until the QTcF returns to < 481 ms. • If QTcF returns to < 481 ms, LEE011 should be reduced by 1 dose level. (please refer to the dosing schedule table) 
Repeat ECGs 7 days and 14 days after dose resumption for any patient who has therapy interrupted due to QTcF ≥ 501 ms
 
 • If QTcF of ≥ 501 ms recurs, discontinue LEE011- Dose limiting toxicity

4 QT/QTc ≥ 501 or > 60 ms change from baseline
 
And
 
Torsades de pointes or polymorphic ventricular tachycardia, or signs/symptoms of serious arrhythmia
	Dose limiting toxicity

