7.0 VISIT SCHEDULE AND ASSESSMENTS

Table 7.1, lists all of the assessments and indicates with an “X”, the visits and when they are performed. For the phase Ib component only the first cycle will be utilized for determination of dose limiting toxicities. All data obtained from these assessments must be supported by the proper source documentation and placed in the patient’s chart.

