3. In order for an accurate evaluation of baseline QTc, a total of three (triplicate) 12-lead ECGs will be performed after resting in a supine position for 5-10 min, with a 2 minute interval between each ECG (triplicate ECG's at screening only). Subsequent ECG's will be performed after resting in a supine position for 5-10 min, on Day 1, C1D15, and C2D15 of each treatment cycle (single ECG's)prior to chemoembolization and LEE011;

4. For all treatment visits there is a general +/- 3 day window on assessments to take into account scheduling over public holidays, if not specifically specified otherwise;
5. Baseline scans can be completed within 28 days prior to registration. After baseline, radiological assessments (CT –chest/abdomen/pelvis or MRI – abdomen/pelvis) must be performed as outline in Table 7.1 (Every 8 weeks during the treatment phase). CT Chest must be performed at baseline. CT Chest during treatment will be performed if clinically indicated. A visit window of +/- 7 days is allowed. Once the patient has been discontinued from the study and enters the efficacy phase, radiological assessments (CT or MRI) will continue on the every 8 weeks schedule until progression or for the first 12 months, whichever comes first. After a year, radiological (CT or MRI) assessments will be performed every 12 weeks until progression.
6. AE/Conmeds will be assessed from consent until up to 30 days last dose of LEE001 or until resolution, whichever comes first. Conmeds will recorded up to 30 day prior to consent;
7. The biopsy performed during screening is for HCC diagnosis and RB positive status and must be performed for the subject to be eligible for the study. However, initial TACE can be performed following agreement of informed consent while RB proficiency is being determined. If patient is not RB proficient patient will be removed from the study as a screen failed and offered other treatment. If the patient has archival formalin fixed paraffin embedded tissue no additional baseline biopsy will be done. The post treatment biopsy is optional and for research purposes only (phase 2 only). If the subject consented to the research biopsy during the consent process, it will be performed during the 8th and 9th week of after initiating treatment of LEE011 and at least one chemoembolization. NOTE: LEE011 should be held for 24-48 hours prior to and after the second biopsy. These held doses will not be made up and noted on the patient's diary.

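### No routine ECG is timed to peak LEE011 exposure: read literally, Table 7.1 footnote 3 puts both on-drug ECGs before that day's dose

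*Combined protocol and SAP*

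**What the plan says.** Table 7.1 marks 12-lead ECGs at screening, Day 1 and Day 15 of cycles 1 and 2, Day 1 of cycle 3 and of every later cycle, end of treatment and safety follow-up. Footnote 3 asks for triplicate tracings at screening only. Later ECGs are taken "on Day 1, C1D15, and C2D15 of each treatment cycle (single ECG's)prior to chemoembolization and LEE011". The footnote mark sits on the screening and C2D15 cells. The C1D15 cell carries no mark, but the footnote text names that visit. No ECG has a clock time or an interval from dosing.

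LEE011 is taken on days 1-21, and "Days 22-28 will be a “rest” from LEE011" (section 6.3). Section 6.4 has patients take it "with a large glass of water (~250 mL or 8 oz.) at the same time each day", with no instruction to hold the dose for an ECG. Footnote 4 states: "For all treatment visits there is a general +/- 3 day window on assessments".

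On kinetics, section 1.7.4.1 says "LEE011 is rapidly absorbed with median T_{max} ranging from 2-5 hours in both adult and pediatric patients" and that the mean effective half-life "was 32.6 hours in study CLEE011X2101". It also gives steady state by about day 8 and 2- to 3-fold accumulation by C1D18.

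The QTc rows of section 6.6 (cycle 1) and Table 6-6 (later cycles and phase II) act at 481 and 501 ms. Table 6-6 refers back to Table 7.1 for when ECGs are done. Section 7.0 adds: "For the phase Ib component only the first cycle will be utilized for determination of dose limiting toxicities".

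**The concern.** The protocol treats QT prolongation as a real risk. Section 1.7.3 reports QTc prolongation in dog telemetry and calls for ECG monitoring in patients. Section 1.7.4 lists lower QTcF risk among the reasons for developing 600 mg when the MTD was 900 mg/day. The routine ECGs that feed the QTc rules nevertheless miss the hours when drug level is highest:

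- C1D1 is before any drug.
- Day 1 from cycle 2 on follows the rest week.
- End-of-treatment and safety ECGs come after the last dose and are not timed to it.
- C1D15 and C2D15 are on drug, but are either pre-dose or untimed.

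A patient whose QTcF crosses a threshold only near peak could be read as normal and continue at full dose. Repeat ECGs do not close the gap, because they are triggered only by an abnormal tracing.

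**Working it through.** **Inputs.** Half-life 32.6 h and Tmax 2-5 h (section 1.7.4.1); once-daily dosing on days 1-21 (section 6.3); visit window of 3 days either way (footnote 4); QT counts at 600 mg (Table 2-2). The one-compartment oral model with first-order kinetics is an assumption.

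**Check against the protocol's own figure.** k = ln 2 / 32.6 = 0.0213 per hour. Accumulation = 1 / (1 − e^(−24k)) = 2.50, inside the stated 2- to 3-fold.

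**Is Day 15 at steady state?** The share of steady-state trough before dosing is 1 − e^(−24k(d−1)). It is 0.996 on day 12, 0.999 on day 15 and 1.000 on day 18. The whole window is on drug and at steady state.

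**Level within a dosing interval.** C(t) is proportional to e^(−kt)/(1 − e^(−24k)) − e^(−ka·t)/(1 − e^(−24ka)). Solving ka for a steady-state Tmax of 2 h or 5 h gives about 1.8 or 0.45 per hour.

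| Time of ECG | Share of peak, Tmax 2 h | Share of peak, Tmax 5 h |
|---|---|---|
| Pre-dose | 0.634 | 0.701 |
| 1 h after dose | 0.962 | 0.845 |
| 2 h | 1.000 | 0.928 |
| 5 h | 0.950 | 1.000 |
| 8 h | 0.891 | 0.972 |
| 12 h | 0.818 | 0.903 |

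Peak is therefore 1/0.701 = 1.43 to 1/0.634 = 1.58 times the pre-dose level. Simple decay, 2^(−(24 − Tmax)/32.6), gives similar shares: 0.626 and 0.668.

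**Day 1 from cycle 2 on.** The last dose is on day 21 and the ECG on day 29, which is 8 × 24 = 192 h. The level is 1.8-2.0% of peak. With the window (120 to 264 h) it ranges from 9% down to 0.4%.

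**Count over six cycles.** 6 Day 1 ECGs + 2 Day 15 ECGs = 8 routine treatment-phase ECGs marked in Table 7.1. One is before any drug, five follow the rest week and two are on drug. None is timed to 2-5 h after a dose.

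**Reported QT events at 600 mg.** Any grade 10/67 = 15% (exact 95% interval 7.4% to 25.7%). Grade 3/4 0/67, exact upper limit 1 − 0.025^(1/67) = 5.4%.

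**What cannot be computed.** The documents give no concentration-QTc slope and no human kinetics for LEQ803, the hERG-active metabolite. The missed prolongation cannot be put in milliseconds.

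**The case against.** **The pre-dose wording may not reach Day 15.** Table 7.1 marks chemoembolization and LEE011 only at Day 1 visits, so the phrase fits Day 1 better, and the footnote sentence is garbled. This stands as a fair alternative reading. It replaces a pre-dose ECG with an untimed one: 1-12 h after an ordinary dose, the reading would see 82-100% of peak. The gap would then be smaller, but unknown, because no clock times are required.

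**Other ECGs may be on drug.** The toxicity evaluation after chemoembolization (end of section 6.12) lists ECGs. If it also applies after a repeat procedure, some could fall on drug. They are not timed to a dose, and Table 7.1 has no ECG mark in that column.

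**Day 15 is informative even pre-dose.** Accumulation of 2- to 3-fold puts first-dose levels at about 1/3 to 1/2 of steady state, below a 63-70% trough. A reader might infer that the plan is blind to on-drug QTc. The documents do not support that.

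**DLT calls are barely touched.** A reader might also infer that dose escalation rests on a mistimed ECG. Section 6.6 does not work that way. For 481-500 ms the rule is "If QTcF ≥ 481 ms recurs, dose limiting toxicity". At 501 ms or more on two ECGs the drug is interrupted and reduced, with a DLT only on recurrence. Torsades, polymorphic ventricular tachycardia or signs of serious arrhythmia with marked prolongation count at once, and catching those clinical events does not depend on the scheduled ECG's hour. If dosing resumes promptly after a C1D15 finding, the 7- and 14-day repeats fall near day 22 (first rest day) and day 29 (off drug).

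**Pre-dose has a merit.** Staff can act on QTcF or low electrolytes before the next dose. This is true, but the loss is one further dose in a patient already at steady state.

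**Conclusion.** The point holds as a minor, cheap improvement to safety monitoring. Under either reading of footnote 3, no routine ECG is timed to the protocol's own Tmax. Under the literal reading, the two on-drug ECGs in Table 7.1 see about 63-70% of steady-state peak, given the one-compartment assumption and the stated half-life. QTc near peak is under-sampled, and detection at the 481 and 501 ms thresholds is less sensitive for the interruption, dose-reduction and discontinuation rules in section 6.6 and Table 6-6.

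The documents do not show that harm follows. No grade 3/4 QT event occurred among 67 patients at the top planned dose, although the exact upper limit is 5.4% and they were not an HCC-specific group. Other safeguards are in place: the screening QTcF limit on triplicate ECGs (5.2.4), the ban on drugs with known QT risk (6.9) and the electrolyte checks in the QTc tables. The PFS analysis is unaffected.

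**What to change.** Amend footnote 3 so that the existing C1D15 and C2D15 ECGs are done 2-5 h after that day's LEE011 dose, taken at the patient's usual time. Record the clock time of the dose and of the ECG. State that Day 1 ECGs stay pre-dose. In the model above, the Day 15 readings would then fall at 93-100% of peak.

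The cost is a one-line amendment and two recorded times per visit, with no added ECG or visit. The Day 15 visit has to be booked around the usual dose time. An abnormal QTcF or electrolyte result would be acted on after that day's dose, so the patient goes once more from about 63-70% to 100% of peak. Cycles 3 onward are unchanged, because Table 7.1 has no Day 15 visit there.

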3.1 ENDPOINTS

Phase Ib:

The primary endpoint of the phase Ib trial will be determination of the maximum tolerated dose of LEE011 administered following chemoembolization (section 6.6).

Phase II:

The primary endpoint of the phase II trial will be progression free survival (PFS) of HCC patients.

Statistics and sample size justification:

PFS is defined to be the time from initiation of treatment to progression or death without evidence of progression. For cases without documentation of progression, follow-up will be censored at the date of last disease assessment without progression, unless death occurs within 4 months following the date of last progression-free, in which case death will be counted as an event. The historical median PFS for TACE alone is 8-10 months. Our institutional median PFS for TACE based on similar chemoembolization procedures as outlined below is 8.0 months. This study will target a hazard ratio of 1.45 with an 80% power and a one-sided significance level of 10%. Assuming a 24-month accrual and an 18-month follow-up period the study requires 40 patients initiating LEE011 treatment with the median PFS for TACE alone is 8 months. PFS will be estimated using the Kaplan-Meier method, and Greenwood's formula will be used to calculate the standard error of the corresponding Kaplan-Meier estimate and 95% confidence interval. Survival curves will be estimated using Kaplan-Meier methodology.

Secondary endpoints of efficacy are to evaluate OS. The same statistical methods used for the analysis of PFS will be used for the analysis of OS.

Other secondary objectives will include description of toxicity of the therapy regimen. These data will be analyzed separately. The safety analyses will be performed on all patients who receive any dose of therapy. Adverse events will be described using the NCI CTCAE v. 4.03 criteria (ctep.cancer.gov/forms/CTCAEv4.pdf). Frequency and severity of adverse events according to the NCI CTCAE v. 4.03 body system and severity criteria will be described. In addition, frequency of Grade 3 or 4 adverse events will be described separately. Causality will also be noted. Adverse events will be recorded for up to 30 days following discontinuation of LEE011 or followed until resolution, whichever comes first. Response rate and toxicity rate will be estimated

using an exact binomial method along with the 95% confidence interval.

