7.1 TABLE OF ASSESSMENTS

Treatment Days	Screening Phase ¹		Treatment Phase: Chemoembolization	Treatment Phase: LEE011						Post Treatment Follow-up			Survival Phase
	Day -28 – Day -1	Day -7 – Day -1	7-14 days Following chemoembolization	Cycle 1		Cycle 2		C3	C4+	End of Treatment or Early Withdrawal (Within 15 Days of Last LEE011 Dose)	Safety Follow-Up (Within 30 Days of Last LEE011 Dose)	Efficacy Follow-Up	Survival Follow-Up Every 12 weeks
Visit Assessments				Day 1 ^{2,13}	Day 15	Day 1	Day 15	Day 1	Day 1				
Informed Consent	X												
Demographics	X												
Eligibility Checklist - Inclusion / Exclusion	X												
Med History	X												
Dx and Extent of Cancer (Staging)	X												
Physical Exam		X	X	X	X	X	X	X	X	X	X		
ECOG Status		X	X	X	X	X	X	X	X	X	X		
Height	X												
Weight		X		X	X	X	X	X	X	X	X		
Vital Signs		X	X	X	X	X	X	X	X	X	X		
CBC		X	X	X	X	X	X	X	X	X	X		

Chemistry (CMP)		X	X	X	X	X	X	X	X	X	X			
Cholesterol/Lipid Panel		X		X	X	X	X	X	X	X	X			
PT/INR		X	X	X	X	X	X	X	X	X	X			
Serum Pregnancy Test (WOCBP Only)		X							X	X				
Urinalysis		X								X	X			
Tumor Assessments with RECIST 1.1 ⁵	X			←----- Every 8 weeks ⁵ ----- -----→									X ⁵	
ECHO/MUGA	X													
ECG (12 – Lead)		X ³		X	X	X	X ³	X	X	X	X			
Adverse Events ⁶	X	X		X	X	X		X	X	X	X			
Conmeds ⁶	X	X		X	X	X		X	X	X	X			
Biomarker Tissue Collection (Biopsy) ⁷	X ⁷					X ⁷								
Biomarker Blood Collection ⁸		X		X		X		X	X	X				
LEE011 Study Drug (Oral) ⁹				X		X		X	X					
Patient Dosing Diary for LEE011 ⁹				X		X		X	X					
Chemoembolization (TACE) ¹⁰				X		X		X	X					
Discontinuation ¹¹											X			
Survival Follow-Up ¹²													X	

1. Screening assessments, apart from those listed above, must occur within 28 days of registration as per Table 7.1;
2. Vital Signs, ECOG Performance Status, Physical Exam, ECG, CBC, CMP, PT/INR, Lipid Panel, Serum Pregnancy Test (WOCBP Only), and Urinalysis should be performed within 7 days of the first treatment day (Cycle 1, Day 1). If there are any dose modifications or halting of drug in the phase II aspect, weekly hematology, comprehensive metabolic panels, and PT/INR laboratory investigations will be performed until the grade of adverse event leading to the modification or cessation is stable or a grade reduction occurs. In addition, following each chemoembolization the following will be done every other week for two cycles after each chemoembolization: physical examination, CMP, CBC, and PT/INR.

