7.4 POST – TREATMENT FOLLOW-UP PHASE

7.4.1 End of Treatment and Early Withdrawal Visit

Patients who completely discontinue study treatment should be scheduled for an End of Treatment (EOT) visit within 15 days following the last dose date of LEE011, at which time all of the assessments listed for the EOT visit will be performed. For details of the assessment, see Table 7-1.

At a minimum, all patients who discontinue study treatment, including those who refuse to return for a final visit, will be contacted for AE evaluations during the 30 days following the last dose date of LEE011.

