7.4.2 Safety Follow-Up

All patients will be followed up for safety up to 30 days after last dose of study drug (LEE011) treatment. Patients whose treatment is interrupted or permanently discontinued due to an AE, including abnormal laboratory value, must be followed until resolution or stabilization of the event, whichever comes first.

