Other secondary objectives will include description of toxicity of the therapy regimen. These data will be analyzed separately. The safety analyses will be performed on all patients who receive any dose of therapy. Adverse events will be described using the NCI CTCAE v 4.03 criteria (ctep.cancer.gov/forms/CTCAEv4.pdf). Frequency and severity of adverse events according to the NCI CTCAE v# body system and severity criteria will be described. In addition, frequency of Grade 3 or 4 adverse events will be described separately. Causality will also be noted. Adverse events will be recorded for up to 1 year following discontinuation from study. Response rate and toxicity rate will be estimated using an exact binomial method along with the 95% confidence interval.

Laboratory assessments will also be described according to the NCI CTCAE v. 4.03 criteria, with separate descriptions for Grade 3 or 4 laboratory abnormalities. Clinically significant laboratory abnormalities will be described as well. Serious adverse events will be summarized, including a causality assessment.

The number of treatment cycles and doses administered will be summarized using descriptive statistics. Treatment delays will be summarized using counts and percentages.

Patients' disposition will be summarized in the following manner:

- The number and percentage of patients selected, included, completed, withdrawn and lost to follow-up will be summarized using descriptive statistics;
- Major protocol deviations will be summarized;
- The reason for withdrawal (adverse events, lack of efficacy, major protocol deviation, non-medical reason, recovery or remission) will be summarized.

For pathology-, laboratory- and imaging-correlative studies, Cox regression analysis will be

conducted to investigate the association between PFS and parameters from correlative studies.

Approximately 175-200 patients with HCC are seen annually at UT Southwestern Medical Center with 80-90 chemoembolizations performed. We anticipate no potential problems meeting the accrual deadlines with the proposed trial. In addition, there are no competing trials either nationally or at UT Southwestern for this patient population that would potential limit accrual.

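### Adverse event recording stops 30 days after LEE011 in five places but runs up to 1 year after leaving the study in section 12.1, and the 30-day rule takes no account of a TACE given after the last dose

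*Combined protocol and SAP*

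**What the plan says.** Five places end AE recording or safety follow-up 30 days after LEE011:

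- Section 3.1: "Adverse events will be recorded for up to 30 days following discontinuation of LEE011 or followed until resolution, whichever comes first".
- Table 7.1, column heading: "Safety Follow-Up (Within 30 Days of Last LEE011 Dose".
- Table 7.1, footnote 6: "AE/Conmeds will be assessed from consent until up to 30 days last dose of LEE001 or until resolution, whichever comes first" (LEE001 is plainly a slip for LEE011).
- Section 7.4.1, which sets a floor: patients "will be contacted for AE evaluations during the 30 days following the last dose date of LEE011".
- Section 7.4.2: "All patients will be followed up for safety up to 30 days after last dose of study drug (LEE011) treatment".

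Section 12.1 otherwise largely repeats the safety paragraph of 3.1, but says: "Adverse events will be recorded for up to 1 year following discontinuation from study".

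Section 6.2 defines study treatment as chemoembolization together with LEE011. Section 9.5 counts its 30 days from the last protocol treatment, but it governs expedited reporting only. Section 6.6, which is the phase Ib section, gives 30 days of safety follow-up after the initial TACE to patients who never receive LEE011.

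**The concern.** Rates of AEs under the combination are secondary objective 2.2.2. A rate needs a defined observation period, and the current text gives two, with different lengths and different starting points.

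The shorter period is also tied to only one of the two study treatments. A patient can have a repeat TACE after the last capsule and then not go back to LEE011. Recording then stops sooner after the TACE than it would after a LEE011 dose, and toxicity from that TACE is observed for a shorter time. A patient who has TACE and never takes LEE011 has no last dose from which footnote 6 can count.

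**Working it through.** **1. The two rules side by side.** The inputs are 30 days after LEE011 (3.1, Table 7.1 heading, footnote 6, 7.4.1, 7.4.2) and up to 1 year after discontinuation from study (12.1).

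- With both clocks started on the same day: 365 − 30 = 335 days. The difference is larger if the patient leaves the study after stopping LEE011.
- Reading both as ceilings does not reconcile them. The shorter rule closes at 30 days or at resolution, whichever is earlier, so it shuts a period that 12.1 leaves open.
- In Table 7.1 the last AE mark is in the safety follow-up column. The efficacy and survival follow-up columns have none, so the 1-year rule has no scheduled assessment behind it.

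**2. Whether TACE can come after the last LEE011 dose.** Section 6.3 gives LEE011 on days 1–21 of 28. The repeat-TACE criteria in 6.12.7 concern toxicity, creatinine, bilirubin and a 4-week spacing, and set no condition on LEE011. Table 7.1 marks TACE at Day 1 of a cycle. The text on LEE011 administration with chemoembolization requires raised liver enzymes to return to baseline grade before LEE011 continues, and footnote 13 treats continuation as a decision made at the post-TACE visit. So a TACE can precede a decision not to resume LEE011.

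**3. Size of the shortfall.** Let L be the day of the last LEE011 dose and T the day of the final TACE, with T later than L.

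- Window closes on day L + 30.
- Days covered after TACE = 30 − (T − L).
- Days short of 30 = T − L.

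With L = 21 (a full cycle), the window closes on 21 + 30 = day 51:

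| TACE on day | Days covered (51 − T) | 30 days after TACE | Days uncovered |
|---|---|---|---|
| 22 | 29 | day 52 | 1 |
| 28 | 23 | day 58 | 7 |
| 29 | 22 | day 59 | 8 |

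The day-29 row assumes TACE on the next nominal Day 1 and LEE011 not resumed.

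**4. The footnote 13 route.** Here the post-TACE visit serves as Day 1. Table 7.1 puts that visit 7–14 days after TACE. With Day 1 on day 29, TACE falls between 29 − 14 = day 15 and 29 − 7 = day 22. The shortfall is at most 22 − 21 = 1 day.

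**5. Patients who never start LEE011.** With no L, footnote 6 cannot be applied. In phase Ib, 6.6 supplies 30 days after the initial TACE. For phase II, the starting criteria following 6.12.6 have patients re-evaluated every 5–7 days and removed if they do not qualify within 28 days, but set no AE recording window.

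**6. Visits already scheduled after TACE.** Footnote 2 says that "following each chemoembolization the following will be done every other week for two cycles after each chemoembolization: physical examination, CMP, CBC, and PT/INR". Two cycles are 2 × 28 = 56 days. For TACE on day 29, this gives visits at about days 43, 57, 71 and 85. Day 57 lies after the written window closes (day 51) and before 30 days after TACE (day 59).

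**The case against.** The best defence is that every visit-level instruction uses 30 days. The outlier is one sentence in the statistics section, in a paragraph that still has an unfilled CTCAE version number. Staff working from Table 7.1 would follow 30 days, so the sentence may be a leftover. That is plausible, and a reader should not infer that 335 days of data would be lost: the figure is a difference between texts. But the sentence is current, it stands in the section that governs the analysis, and nothing marks it as superseded.

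On TACE, the defence is that the sequence is particular and largely covered elsewhere. Open events are followed under 7.4.2 and 9.3. Serious events have their own route in 9.3.3. Section 9.5 brings events within 30 days of protocol treatment, and later attributed ones, into expedited reporting. Section 7.4.1 is only a minimum: "At a minimum, all patients who discontinue study treatment, including those who refuse to return for a final visit, will be contacted for AE evaluations". Section 10 collects AEs at every visit, which could be read to include the footnote 2 visits. Most of this stands. It does not move the end date in footnote 6, and footnote 2 itself lists an examination and laboratory tests only.

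For patients who never start LEE011, the defence is that they may not count. Section 8.2 limits safety analyses to those with at least one dose of study drug. Sections 3.1 and 12.1, however, include anyone who received any dose of therapy, so the question is open.

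Two stronger readings are tempting:

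- **A limit on the shortfall.** A reader might take the 4-week limit on toxicity interruptions in 6.5 to mean that at least 30 − 28 = 2 days are always covered after TACE. It does not. The section does not say when the 4 weeks start. Counted from the first missed dose after the 7-day rest, TACE could fall 7 + 28 = 35 days after the last dose, beyond the window altogether. The limit also applies only to interruptions for toxicity.
- **Visits without AE collection.** A reader might infer from apparently empty AE cells in Table 7.1 that some treatment-phase visits omit AE collection. The table layout is not a reliable basis for that, and section 10 requires collection at every visit.

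**Conclusion.** The inconsistency is certain: section 12.1 contradicts five other places, and no scheduled AE assessment would deliver its rule. The LEE011-only anchor is a real but small mismatch with the definition of study treatment. Under the written rule, a final TACE after the last dose is followed for fewer than 30 days: 8 days short in the day-29 example, and at most 1 day short by the footnote 13 route. Both figures assume a full 21-day course, and the day-29 figure also assumes that LEE011 is not resumed. A LEE011 hold before TACE would lengthen the shortfall. The documents do not show how many patients would be affected.

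Severity is minor. What could go unrecorded is mainly new non-serious AEs. The documents do not support a claim that serious TACE toxicity would escape reporting.

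**What to change.** Replace the 1-year sentence in 12.1, and write one rule into 3.1, the Table 7.1 heading, footnote 6, 7.4.1, 7.4.2 and 12.1:

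- Record AEs to 30 days after the later of the last LEE011 dose and the last TACE.
- For patients who have TACE and never start LEE011, in both phases, record AEs to 30 days after the initial TACE.

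The cost is wording in six places and slightly longer AE recording for patients whose last treatment is TACE. In the day-29 example the close moves from day 51 to day 59, and the footnote 2 visit near day 57 falls in the added period, so no new visit is needed. For phase II patients who never start LEE011, the end date is at most 30 − 28 = 2 days beyond the existing re-evaluation period.

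Dropping the 1-year rule gives up late non-serious AEs on paper, but no scheduled assessment would have collected them. Section 9.5 still requires later events attributed to the agents to be reported.
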